5.10 Withdrawal/follow-up

Withdrawal, lost-to-follow-up and missed assessments of the primary outcome will be reported in the flowchart, separately for randomized to Amulet and randomized to Watchman.

CTU Bern	Swiss APERO SAP	Version: 2.0	
	Template: CS_STA_TEM-11	Valid from: 17.08.2021	

6. Analysis

6.1 Outcome definitions

Outcomes will be compared randomized to Amulet vs randomized to Watchman.

6.1.1 Primary outcome

The primary outcome is the composite of LAA patency at 45 day CCTA or the crossover from one device to the other device based on morphological/anatomical considerations during device implantation.

6.1.2 Secondary outcome

Secondary outcomes are:

- *LAA patency (arterial and/or venous phase) at 45 day CCTA and 13-month CCTA in the per protocol and as treated populations*
- *All cause of death, stroke, systemic or pulmonary embolism and spontaneous MI*
- *Cardiovascular death*
- *Ischemic stroke*
- *Hemorrhagic stroke*
- *Bleeding events according to the BARC classification at each follow-up.*
- *Procedure-related complications*
- *Rate of patients on (N)OAC at 45 days and 6 months*
- *Device related thrombosis at 45 day TEE/CCTA and 13-month CCTA in the per protocol and as treated populations*
- *Feasibility outcome (number of device implantation attempts, total time procedure, x-ray dose and total contrast dose used in the procedure)*
- *LAA patency at 45 day TEE in the per protocol and as treated populations*

6.1.3 Safety outcome

The main safety outcomes are:

- *Bleeding Academic Research Consortium (BARC) bleeding grade 2, 3 and 5 up to 48 hours or discharge whichever comes first and 45 days*

CTU Bern	Swiss APERO SAP	Version: 2.0	
	Template: CS_STA_TEM-11	Valid from: 17.08.2021	

- *Net adverse clinical events (NACE) defined as the composite of death, fatal and non-fatal stroke, peripheral embolization and BARC 2, 3, or 5 up to 48 hours or discharge whichever comes first and 45 days*
- *Device related thrombosis at 45 day TEE/CCTA and 13-month CCTA in the per protocol and as treated populations*

6.1.4 Feasibility outcome

A composite of following outcomes will be analysed in order to assess the feasibility of two devices:

- *Number of attempts of LAA closure with a single device.*
- *Number of same type device used in a procedure.*
- *Total time procedure, x-ray dose and total contrast dose used in the procedure.*

6.2 Analysis methods

6.2.1 Primary analysis

The primary outcome analysis will be conducted by measuring the LAA patency at 45 days using the CCTA, combined with adjudicated cross-over including failed cross-over to another non-randomized LAAC device during the index LAAC procedure.

6.2.2 Secondary analyses

Secondary analyses of events at longer follow-ups (e.g. 1 to 5 years of follow-up) will be conducted using Cox's regressions comparing the randomized arms (hazard ratios with 95% confidence intervals) and reporting event rates (from Kaplan-Meier estimates accounting for lost-to-follow-up and withdrawal of consent). In most cases only the first event of each event (sub)type will be reported, except if requested otherwise and the statistical analyses will be adapted to a multi-event analyses design.

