3. BACKGROUND AND RATIONALE

3.1 Background and Rationale

Atrial fibrillation (AF) is the most common cardiac arrhythmia and a major cause of morbidity and mortality because of cardioembolic stroke. The prevalence of AF increases with age up to 15% in high octogenarians and continues to grow rapidly because the proportion of the aging population is increasing just as the prevalence of predisposing conditions for AF such as diabetes, heart failure, hypertension, and coronary heart disease⁶. Cardiac embolism because of AF causes up to 25% of all ischemic strokes, which makes it socioeconomically highly relevant⁷. Oral anticoagulation (OAC) with vitamin K antagonists (VKA) or Non-vitamin K antagonist anticoagulant (NOAC) is the most effective prophylaxis for stroke in AF. Yet, (N)OAC therapy is associated with a significant bleeding liability and long-term (N)OAC therapy in patients with NVAF and concomitant high bleeding risk poses safety issues in a sizable and growing population in clinical practice. Postmortem and echocardiographic studies have shown that the vast majority of all cardiac thrombi in patients with AF form in the left atrial appendage (LAA)⁸. Thus, a reasonable alternative is the exclusion of the LAA cavity from the circulation.⁹

Currently, the Amplatzer ACP/Amulet™ (St. Jude Medical-Abbott), and the Watchman™ (Boston Scientific, Natick, MA, USA) are the devices with most clinical experience reported to date for percutaneous closure of LAA. The Watchman was tested in the setting of two randomized control trials. The PROTECT AF¹⁰ (Percutaneous closure of the left atrial appendage versus warfarin therapy for prevention of stroke in patients with atrial fibrillation: a randomised non-inferiority trial) trial was a multicentre, randomized controlled trial in NVAF patients comparing the Watchman device to warfarin for a composite primary endpoint of stroke, systemic embolism, and cardiovascular (CV) death. Noninferiority to warfarin was documented early and long term (2,621 patient-years [PY]), LAA closure (LAAC) demonstrated a significant (40%) relative risk reduction to warfarin for the primary efficacy endpoint, an 85% relative risk reduction in hemorrhagic stroke, a 60% relative reduction in CV mortality

(absolute annual risk reduction of 1.4%), and a 34% relative reduction in all-cause mortality (absolute annual risk reduction of 1.6%).

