5.2 Secondary Outcomes

Secondary end-points include¹:

- LAA patency (arterial and/or venous phase) at 45-day and 13-month CCTA in the per protocol and as treated populations
- All cause of death, stroke, systemic or pulmonary embolism and spontaneous MI
- Cardiovascular death
- Ischemic stroke
- Haemorrhagic stroke
- Bleeding events according to the BARC classification at each follow up.
- Procedure-related complications²
- Rate of patients on (N)OAC at 45 days and 6 months
- Device related thrombosis (DRT) at 45 day TEE/CCTA and 13-month CCTA in the per protocol and as treated populations
- Feasibility outcome (number of device implantation attempts, total time procedure, x-ray dose and total contrast dose used in the procedure)
- LAA patency at 45 day TEE in the per protocol and as treated populations

Adverse clinical events will be assessed at up to 48 hours or discharge whichever comes first, at 45 days, and yearly.

¹ For the definitions of endpoint and adverse clinical events see the Appendix 1.

²As defined in 5.3.

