12.4 Planned Analyses

Datasets to be analysed, analysis populations

The main analysis of the primary endpoint will be conducted on all randomized patients who have completed the 45-day follow-up according to the intention to treat principle, in keeping with the superiority prespecified study hypothesis. Additional analyses of the primary endpoint will be also carried out in the per-protocol and as-treated populations. Similarly, LAA patency and DRT at 45-day and 13-month CCTA and at 45-day TEE **as well as clinical outcomes** will also be analyzed in the per-protocol and as-treated population.

Primary and secondary Analysis

Primary and secondary end points will be analysed on an intention-to-treat basis; as above mentioned some of them will be analysed also in the per-protocol and as-treated populations. Categorical outcome measures will be compared using a χ^2 test or Fisher exact test as required. Continuous variables will be compared using a 2-sided unpaired t test or a Mann-Whitney test, as appropriate. Estimation of the cumulative incidence of safety and efficacy endpoints will be performed using the Kaplan-Meier method, and event rates will be compared by the log rank test. The estimated relative risk (RR) is the ratio of the risk probabilities, and a confidence interval will be constructed based on a logarithmic transformation. Correlations between variables will be analyzed with a Cox regression.

Interim analyses

No statistical interim analyses planned.

Safety analysis

No statistical interim analyses planned.

Deviation(s) from the original statistical plan

Any deviation from the planned analyses will be reported in the final trial report.

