2.6 Timing of final analysis

The primary endpoint analyses will be performed after all 45 days follow-up visits are conducted and completely entered into the data capture system; and after all data are cleaned and events have been adjudicated. Longer follow-up analyses at e.g. 13 months, 2 years, 3 years, 4 years and 5 years will be conducted as requested, after all data have completely entered into the data capture system; and after all data are cleaned and events have been adjudicated.

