3.3 Data preparation

LAA patency is derived from the average Linear attenuation coefficient within the LAA distal to the device's lobe (artphase_mean2) ≥ 100 HU OR average Linear attenuation coefficient within the LAA distal to the device's lobe $\geq 25\%$ of the average Linear attenuation coefficient within the LAA (artphase_mean2/artphase_mean1 ≥ 0.25), as recorded inside the follow-up 45 days visit of the Consensus estimate (this is the consensus of the three Core laboratory assessments by three different assessors). LAA patency is a marker of leaks in/out of the LA and therefore a marker of potential thrombus material migration from the LAA to blood circulation system.

Cross-overs are captured in the procedure eCRF and Adjudicated by the clinical event adjudication committee, both successful and failed attempts to cross-over.

CTU Bern	Swiss APERO SAP	Version: 2.0	
	Template: CS_STA_TEM-11	Valid from: 17.08.2021	

The primary endpoint is defined as LA patent or adjudicated cross-overs including failed cross-overs.

Table 1: Derivation of LA patency used in the primary outcome.

Outcome	eCRF sheet	Variable	Variable type	Remarks
LAA patency				
patent = 1	CCTA	fu_reader = 6 = Consensus AND (artphase_mean2 ≥ 100 OR artphase_mean2/artphase_mean1 ≥ 0.25)	Categorical Continuous	Consensus assessment of three assessors LAA HU mean distal from device's lobe in arterial phase = artphase_mean2 LA HU mean in arterial phase = artphase_mean1
not patent = 0				artphase_mean2 not missing and not patent as reverse of the above

Clinical events are also adjudicated and these adjudicated events up to 45 days after the LAAC procedure (or randomization date if no procedure was initiated) will be analysed, excluding events occurring before the LAAC procedure (or randomization date if no procedure was initiated) and excluding events occurring on day 46 and later. Adjudicated events beyond 45 days are used for the longer-term follow-up analyses and censored accordingly (e.g. at 1 year, at 5 years).

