4.1 Confidence intervals and *P* values

Primary and secondary end points will be analysed on an intention-to-treat basis. Additional analyses will be also carried out in the per-protocol and as-treated populations. Categorical outcome measures will be compared using a χ^2 test or Fisher exact test as required. Continuous variables will be compared using a 2-sided unpaired t test or a Mann-Whitney test, as appropriate. Estimation of the cumulative incidence of safety and efficacy end-points will be performed using the Kaplan-Meier method in case of time-to-event endpoints, and event rates will be compared by the log rank test. The estimated relative risk (RR) is the ratio of the risk probabilities, and a confidence interval will be constructed based on a logarithmic transformation.

The primary endpoint LAA patency or adjudicated cross-over including failed cross-over to other device at 45 days will be analyzed using risk ratios and risk differences.

All statistical tests will be performed using a 5% significance level.

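### Death is not treated as a competing event in the 1- to 5-year Kaplan-Meier rates; if event-free deaths are censored, absolute stroke, bleeding and cardiovascular-death incidence is overstated

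*Combined protocol and SAP*

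**What the plan says.** Protocol 12.4 sets the general method: "Estimation of the cumulative incidence of safety and efficacy endpoints will be performed using the Kaplan-Meier method", with a log-rank comparison. SAP 4.1 repeats it, limited to time-to-event data: "Estimation of the cumulative incidence of safety and efficacy end-points will be performed using the Kaplan-Meier method in case of time-to-event endpoints".

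For longer follow-up, SAP 6.2.2 plans Cox hazard ratios between randomized arms and "reporting event rates (from Kaplan-Meier estimates accounting for lost-to-follow-up and withdrawal of consent". It adds: "In most cases only the first event of each event (sub)type will be reported". The only other censoring rule is in SAP 3.3: "Adjudicated events beyond 45 days are used for the longer-term follow-up analyses and censored accordingly (e.g. at 1 year, at 5 years". SAP 2.6 makes these analyses optional: "Longer follow-up analyses at e.g. 13 months, 2 years, 3 years, 4 years and 5 years will be conducted as requested".

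The secondary endpoints in Protocol 5.2 include cardiovascular death, ischaemic stroke, haemorrhagic stroke and "Bleeding events according to the BARC classification at each follow up", beside a composite that contains all-cause death.

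The sections where a rule on death might sit do not give one:
- SAP 4.3 (estimands) covers only the primary outcome.
- SAP 6.2.5 (assumptions) checks only proportional hazards.
- SAP 6.4 and Protocol 12.5 (missing data) do not mention death.

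**The concern.** Kaplan-Meier assumes that a censored patient could still have the event later. A patient who has died cannot. When event-free deaths are censored, 1-KM estimates the risk in a hypothetical setting without death from other causes, and it lies above the proportion of patients who actually have the event. The gap widens with follow-up and with mortality.

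Four secondary endpoints do not contain all-cause death and are exposed: ischaemic stroke, haemorrhagic stroke, BARC bleeding and cardiovascular death. For cardiovascular death only non-cardiovascular death competes, because Appendix 1, 17.2 counts deaths of unknown cause as cardiovascular.

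At stake are the absolute 1- to 5-year rates of these endpoints. Unlike sampling error, this error runs in one direction, is not reflected in the confidence interval and does not shrink with more patients. The silence also leaves a programming choice open. SAP 6.7 requires the primary and secondary outcomes to be double-programmed, and two programmers could both follow the text and reach different rates.

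**Working it through.** The plan states no long-term event rate or mortality, so there is no figure of its own to reproduce. The check asks how far 1-KM with deaths censored would lie above the cumulative incidence.

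**Inputs from the documents**
- All stroke: 1.2 per 100 patient-years (PY), from the meta-analysis cited in Protocol 3.4.
- Mortality: implied by the Watchman-versus-warfarin trial described in Protocol 3.1, which gives a 60% relative reduction in cardiovascular mortality and then "absolute annual risk reduction of 1.4%), and a 34% relative reduction in all-cause mortality (absolute annual risk reduction of 1.6"% per year. If the relative reduction is r and the absolute reduction is a, the device-arm rate is a/r − a.
  - All-cause: 1.6/0.34 − 1.6 = 3.11 per 100 PY (2.94 to 3.28 allowing for rounding).
  - Cardiovascular: 1.4/0.60 − 1.4 = 0.93 per 100 PY.
  - Non-cardiovascular: 3.11 − 0.93 = 2.17 per 100 PY (from unrounded values).

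**Assumed inputs**
- Bleeding at 2, 5 or 8 per 100 PY.
- Higher mortality of 8 or 12 per 100 PY.
- Constant hazards throughout.

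**Formulas**, with event hazard h, competing-death hazard d and time t:
- 1-KM with deaths censored = 1 − exp(−ht)
- Cumulative incidence = h/(h+d) × [1 − exp(−(h+d)t)]

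Example, all stroke at 5 years: 1 − exp(−0.06) = 5.82%; 0.012/0.0431 × [1 − exp(−0.2155)] = 5.40%; excess 0.43 points.

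Using all deaths as competing gives an upper value, because fatal strokes and deaths after a first stroke do not compete. Each stroke patient dies at most once, so if both rates described the same patients, at least 3.1 − 1.2 = 1.9 per 100 PY would be stroke-free deaths. That gives the lower value.

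**Results at 5 years**

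| Endpoint, rate per 100 PY | Competing deaths per 100 PY | 1-KM | Cumulative incidence | Excess (points) |
|---|---|---|---|---|
| All stroke, 1.2 | 3.11 | 5.82% | 5.40% | 0.43 |
| All stroke, 1.2 | 1.91 | 5.82% | 5.56% | 0.27 |
| Cardiovascular death, 0.93 | 2.17 | 4.56% | 4.32% | 0.24 |
| Bleeding, 2 (assumed) | 3.11 | 9.52% | 8.83% | 0.7 |
| Bleeding, 5 (assumed) | 3.11 | 22.12% | 20.55% | 1.6 |
| Bleeding, 8 (assumed) | 3.11 | 32.97% | 30.69% | 2.3 |
| All stroke, 1.2 | 8 (assumed) | 5.82% | 4.81% | 1.0 |
| All stroke, 1.2 | 12 (assumed) | 5.82% | 4.39% | 1.4 |
| Bleeding, 5 (assumed) | 8 (assumed) | 22.12% | 18.4% | 3.7 |
| Bleeding, 5 (assumed) | 12 (assumed) | 22.12% | 16.8% | 5.3 |

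The bleeding rows, and the stroke rows at 8 and 12, are upper values for the mortality shown: BARC 5 bleeds and fatal strokes are themselves events.

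**Earlier times.** At 3.11 deaths per 100 PY or the lower 1.91, the stroke excess is 0.10 to 0.16 points at 3 years, 0.01 to 0.02 at 1 year and below 0.001 at 45 days.

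**Scale.** With 100 patients per arm and complete follow-up, the 95% half-width for a 5.4% rate is 1.96 × √(0.054 × 0.946/100) = 4.4 points. For a difference between arms it is 1.96 × √(2 × 0.054 × 0.946/100) = 6.3 points.

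**The case against.** **The bias is conditional.** SAP 6.2.2 names loss to follow-up and withdrawal, and SAP 3.3 names the analysis horizon. Neither lists death as a reason for censoring. On a literal reading, a patient who dies event-free could stay in the risk set to the horizon, which would approximate the cumulative incidence. This stands: the upward error follows from usual practice, not from a stated rule. The literal reading would, however, change what the Cox hazard ratio means, so the handling of death needs stating either way.

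**The effect is small beside sampling error.** At the document-based mortality the stroke excess is at most about a tenth of the 4.4-point half-width, and the analyses are run on request. This also stands, and it limits the importance of the point.

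**1-KM is a legitimate descriptive choice.** SAP 6.2.2 speaks of event rates, and a labelled 1-KM beside a Cox hazard ratio is coherent. This stands in part. SAP 4.1 and Protocol 12.4 nonetheless name cumulative incidence as the quantity, and the plan contains no such label.

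**The inputs are borrowed.** Mortality comes from a trial against warfarin and the stroke rate from a separate meta-analysis. This trial enrols high-bleeding-risk patients with no upper age limit. The 1.2 per 100 PY is for all stroke, while the listed endpoints are ischaemic and haemorrhagic stroke separately, so each has a smaller absolute excess at the same mortality. All of this stands. The figures are illustrations.

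**Stronger readings.** A reader might infer that the device comparison is compromised. The documents do not support that: with deaths censored, Cox and log-rank are valid cause-specific comparisons. A reader might also infer that the 5-year rates will be badly overstated. That needs mortality or bleeding rates that the documents do not contain. Nor do they establish that the excess is always slight, since the 1.6-point bleeding figure is a ceiling only at 3.1 deaths per 100 PY.

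**Conclusion.** The point holds as a minor one. The plan pairs cumulative incidence with Kaplan-Meier and does not treat death as a competing event. If event-free deaths are censored, the absolute rates of ischaemic stroke, haemorrhagic stroke, BARC bleeding and cardiovascular death are overstated, increasingly so towards 5 years.

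The size is uncertain because this population's mortality is not given. At the borrowed mortality the excess is a fraction of a point for stroke and cardiovascular death; for bleeding at the assumed 5 per 100 PY it is below two points. At the higher assumed mortalities it could reach about one point for stroke and several for bleeding. All figures rest on constant hazards.

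The primary endpoint, all-cause death and composites containing it are not affected. SAP Table 4 gives the 45-day outcomes as counts with Fisher tests, so they are not affected either. No planned test and no sample size changes.

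**What to change.** In SAP 4.1 and 6.2.2:
- For time-to-event endpoints that do not contain all-cause death, report Aalen-Johansen cumulative incidence with death as the competing event. For cardiovascular death, the competing event is non-cardiovascular death.
- Label the Cox and log-rank results cause-specific, with event-free deaths censored.
- Keep Kaplan-Meier for all-cause death and composites containing it.

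The cost is SAP wording. Appendix 1, 17.2 already classifies every death as cardiovascular or non-cardiovascular, so no new data are needed, and the Stata and R versions in SAP 6.6 can produce the estimates. The small downside is less direct comparability with earlier reports that used 1-KM, which can be tabulated alongside.

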6.2.3 Sensitivity analyses

The primary and secondary outcomes will be analyses in multiple imputed data-sets using chained equations and combining estimates and p-values using Rubin's rule, if requested. It will also be explored whether delayed 45 days visit CCTA assessments (scheduled was 45 days \pm 7 days, but e.g. delays can be due to e.g. the SARS-CoV-2 pandemic forcing postponement of some clinical visits) impacted the primary outcome comparison Amplatzer vs Watchman, by adding the delay in days of the follow-up CCTA as a covariate in the analyses.

CTU Bern	Swiss APERO SAP	Version: 2.0	
	Template: CS_STA_TEM-11	Valid from: 17.08.2021	

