Study Product / Intervention:	
The WATCHMAN (Atritech, Boston Scientific, Natick, MA, USA) LAAC technology consists of the Access System (Access Sheath and Dilator) and Delivery System (Delivery Catheter and WATCHMAN Device). The Access System and Delivery System permit Device placement in the left atrial appendage (LAA) via femoral venous access and inter-atrial septum crossing into the left atrium. WATCHMAN device is a self-expanding nitinol structure with a porous covering on the proximal face. The device is constrained within the Delivery System until deployment in the LAA. The Device is available in 5 sizes from 21 to 33 mm. The new generation Watchman FLX has a shorter device length and a less taper angle to simplify implantation and to fit a wider range of patients. Furthermore, the frame of the new device is designed to enhance sealing within the left atrial appendage.
 
The AMPLATZER Amulet (St. Jude Medical-Abbott) is a self-expanding device made of nitinol that has a distal lobe and a proximal disc, connected by an articulated waist. The device lobe has six to 10 pairs of stabilising wires and is meant to be implanted in the proximal 10-15 mm of the left atrial appendage (LAA), whereas the device disc is intended to cover the ostium at the left atrial side. The proximal female screw is recessed to minimise thrombus formation on the disc and potentially facilitate re-attachment of the device to the pusher screw. The lobe sizes range from 16 to 34 mm.

Number of Participants with Rationale:	
Total number of patients with primary endpoint assessment: 200 100 patients in the Watchman/FLX group 100 patients in the Amplatzer Amulet group Sample size is calculated to state superiority of Amplatzer Amulet compared with Watchman/FLX

Study Duration:	8 years
Study Schedule:	February 2018 February 2026

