A critical step for each LAA closure procedure is the appraisal of LAA residual or new patency/leaks after device implantation. Kanderian et al¹³ showed a trend towards a decreased risk of post procedural cerebral embolism in patients with successful LAA surgical closure as compared to patients with a peridevice leak >1cm assessed with trans-esophageal echocardiography (TEE) at 8 months after intervention. In the setting of available randomized trials (currently only limited to the Watchman device), successful closure was defined by the presence of a peridevice flow ≤ 5 mm assessed with TEE 45 days after the procedure. In these trials, as well as according to the current instruction for use of Watchman, the appraisal of residual leaks 45 days after LAAC was/is considered mandatory for a correct postprocedural management of pharmacotherapy (in terms of continuation or reinstitution of OAC therapy). Whether a similar practice should be implemented after Amulet or other devices is still unclear given the lack of controlled randomized data comparing this specific device with current standard of care consisting of oral anticoagulation. It is relevant to emphasize here that while across pooled Watchman trials there is no clear evidence that the presence or the size of peridevice leaks are associated to higher risk of stroke or systemic embolism, the protocols have mandated the continuation or re-institution of OAC therapy in all cases where a leak of 5 mm or greater was observed at the end of the procedure or at follow-up. Therefore, it remains highly probable that the risk associated to the presence of peridevice leaks has been mitigated by the concomitant use of this imaging-based pharmacological intervention.

Furthermore there is a growing attention to the natural history of peridevice leaks. Freixa et al¹⁴ showed that among twenty-five patients treated with LAAC, the two patients with major leaks after device deployment did not show significant leaks at follow-up (8 months after procedure) whereas the two patients with major leak at follow-up did not show significant leaks after device deployment. Given the unpredictable evolution of peridevice leaks, it is becoming clear the need for a long term imaging follow-up (both short and long-term after LAAC).

[figure not shown]

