- Assessment of SAE and AESI as defined in 11.1 and Appendix 1
- 12 lead ECG
- TEE will be performed at 45 days. TEE could be repeated at 6 and 13 months after procedure if clinically indicated (in case of an intra-cardiac thrombus or/and a PDL >5 mm are revealed at 45 days) according to current standard of care
- CCTA at 45 days and at 13 months after procedure will be performed as study specific interventions.

In the event of pandemic or any other condition for which the participation to follow-up visits would put at risk the health of the patients and/or of the medical staff, the hospital visits will be replaced by phone call. Furthermore, the performance of imaging follow-up outside of protocol temporal window will be allowed.

If a phone call is performed instead of an hospital visit, the following data will be collected:

- Vital status
- Assessment and reporting of adverse clinical events as defined in 9.1.8 and Appendix 1
- Assessment and reporting of SAEs and AESI
- Assessment and reporting of pharmacotherapy, and additional interventions received since last contact.

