12.2 Determination of Sample Size

Considering an incidence of the primary composite end-point in the range of 50% in the Watchman/FLX group, which is a conservative estimate based on previous reports, we estimate that 200 patients will provide greater than 80% power to prove superiority of Amulet as compared to Watchman/FLX assuming a 40% risk reduction (i.e. corresponding to an event rate in the range of 30%) and a significance level of 5% (alpha).

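### The only planned check on late 45-day CCTAs, delay as a covariate, cannot show whether the Amulet versus Watchman/FLX difference changes with delay; an in-window estimate should be added

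*Combined protocol and SAP*

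**What the plan says.** - The study schedule in both documents sets the 45-day visit at 45±7 days, that is day 38 to day 52. The primary objective is occlusion on CCTA 45 days after implantation.
- Protocol 9.1.4 lifts the window in a pandemic or any other condition in which visits would endanger patients or staff. In that case "the performance of imaging follow-up outside of protocol temporal window will be allowed". No latest day is given.
- SAP 3.3 derives patency from the core-laboratory CCTA "as recorded inside the follow-up 45 days visit of the Consensus estimate", without a date condition. The same section does cut clinical events at day 45.
- The per-protocol exclusions in SAP 4.2.2 do not mention scan date, and the subgroups in SAP 6.2.4 include no split by scan timing.
- SAP 6.2.3 contains the one check on timing. It will explore whether delayed scans "impacted the primary outcome comparison Amplatzer vs Watchman, by adding the delay in days of the follow-up CCTA as a covariate in the analyses". No regression model, interaction, in-window analysis or maximum delay is named.
- SAP 4.2 states that crossover patients count as primary events in every analysis.

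**The concern.** The protocol itself gives a reason to care about scan day. Section 3.1 argues for imaging at more than one time point with the words "Given the unpredictable evolution of peridevice leaks", and a 13-month CCTA is planned to follow leaks over time. A scan taken months late may therefore describe a different state from the one in the objective.

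SAP 6.2.3 asks the right question: did delay affect the comparison between devices? The method it names answers a different one. If the device difference in late scans is smaller or larger than at day 45, the all-scan estimate is a mixture of the two. The covariate model reports nearly the same mixture, and an unchanged estimate could be read as reassurance that timing did not matter.

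**Working it through.** **Inputs from the documents.** Protocol 12.2 takes "Considering an incidence of the primary composite end-point in the range of 50% in the Watchman/FLX group", with 30% under Amulet and alpha 5%. The synopsis gives "100 patients in the Watchman/FLX group 100 patients in the Amplatzer Amulet group". The window is day 38–52.

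**Inputs assumed, because the documents give none.** Share of late scans f; event rates in late scans; delay independent of arm, zero for in-window scans and uniform from 8 to 120 days for late ones; two-sided test.

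**1. The plan's own figure.** Power = Φ{[0.20√100 − 1.96√(2×0.4×0.6)] / √(0.5×0.5 + 0.3×0.7)} = Φ{(2.000 − 1.358)/0.678} = Φ(0.947) = 82.8%. This agrees with the statement that "we estimate that 200 patients will provide greater than 80% power to prove superiority of Amulet as compared to Watchman/FLX".

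**2. Why the covariate leaves the contrast in place.** In a linear model with device and delay, least squares gives exactly:

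unadjusted difference − adjusted difference = (delay coefficient) × (mean delay under Amulet − mean delay under Watchman/FLX).

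Randomisation should make the last bracket close to zero, so the two estimates nearly coincide whatever happens to the device difference in late scans.

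**3. What the all-scan estimate measures.** Overall difference = (1 − f) × 20 points + f × late difference. If the late difference is zero:
- f = 20%: 0.8 × 20 = 16 points
- f = 30%: 0.7 × 20 = 14 points

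With late rates of 40% in both arms, power at 100 per arm is 63.8% and 52.4%. If the late difference is 10 points, the overall difference is 18 and 17 points and power is 74.2% and 69.2%. A late difference above 20 points would enlarge the estimate instead.

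**4. Simulation** (1000 trials of 100 per arm, linear risk-difference model, robust standard errors; mean device estimates, Amulet minus Watchman/FLX):

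| Late share | Late rates, Watchman/FLX vs Amulet | No covariate | Delay covariate | Interaction model at zero delay | In-window only |
|---|---|---|---|---|---|
| 20% | 50% vs 30% | −0.202 | −0.202 | −0.203 | −0.203 |
| 20% | 40% vs 40% | −0.159 | −0.160 | −0.190 | −0.200 |
| 30% | 50% vs 30% | −0.201 | −0.201 | −0.200 | −0.201 |
| 30% | 45% vs 35% | −0.174 | −0.174 | −0.197 | −0.206 |
| 30% | 40% vs 40% | −0.140 | −0.140 | −0.184 | −0.200 |
| 30% | 30% vs 30% | −0.138 | −0.139 | −0.183 | −0.200 |
| 40% | 40% vs 40% | −0.123 | −0.123 | −0.177 | −0.199 |

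Adding delay moved the device estimate by 0.003 to 0.005 on average in absolute terms, with or without dilution.

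**5. What the alternatives can do.** The delay coefficient was significant in 23–26% of trials when late rates were 30% in both arms. It was significant in only 5–7% when they were 40% in both arms, where overall patency does not change. The interaction test was significant in 19–26% of trials with no late device difference and in 8–9% with a halved one. Estimates with intervals are therefore more useful than that p-value. In-window power is 73.7% with 80 per arm and 67.9% with 70 per arm.

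**6. Crossovers in an in-window composite.** Suppose 10 of 100 Watchman/FLX patients cross over, 40 of the other 90 are patent, 30% of scans are late and lateness has no effect. Keeping every crossover but dropping late non-crossovers gives (10 + 28)/(10 + 63) = 38/73 = 52.1%, although the true rate is 50%. With no Amulet crossovers that arm stays at 30%, so the difference reads 22.1 points instead of 20. Combining the parts as 10/100 + (90/100) × (28/63) = 0.10 + 0.40 returns 50%.

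**The case against.** The strongest reply is that the plan is less exposed than it looks. The waiver applies only under health-risk conditions. SAP 6.2.3 is exploratory, and it neither plans nor excludes an interaction. Delay in days is recorded, so an in-window analysis could be run later. A delay main effect also has real uses. The 13-month CCTA gives a second look at the device difference, though as a secondary outcome in the per-protocol and as-treated populations. All of this stands. It limits the consequence, but it does not make the named method answer the stated question.

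Three stronger readings are tempting, and the documents do not support them:

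- **That the primary scan has no time limit at all.** Day 52 is the nominal limit. What is missing is a latest day once the limit is waived, and any date condition in the endpoint derivation.
- **That the covariate model discards crossovers who have no CCTA.** SAP 4.2 keeps crossovers as events in all analyses. The gap is narrower: no rule says what delay value such a patient receives.
- **That late scans will hide a real difference.** The unpredictability remark in protocol 3.1 follows a series of 25 patients comparing leaks after deployment with leaks at 8 months. It says nothing about attenuation-based CCTA patency, about one device against another, or about day 45 against a somewhat later day. Late scans could shrink the difference, enlarge it or leave it alone.

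**Conclusion.** The concern holds in a limited form. The check in SAP 6.2.3 can correct for unequal delay and can show an overall drift in patency. It cannot show a device difference that varies with delay, in either direction. This follows from the form of the model when delay is balanced between arms, and does not depend on the assumed rates.

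The size of the effect on this trial is unknown. The falls from 20 points to 16 or 14 are illustrations that assume 20% or 30% late scans with no device difference among them. They also treat the whole composite as time-dependent. Crossovers occur at the procedure, so only the patency component can change with scan day. This is a low-cost improvement to a sensitivity analysis, and the main analysis is not faulted.

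**What to change.** Keep the delay covariate, since it is the only planned adjustment for arm imbalance in timing, and add to SAP 6.2.3:

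1. **An in-window (day 38–52) estimate by allocated arm**, for LAA patency and for the composite. In each arm, form the composite as the crossover proportion among all randomised patients, plus the non-crossover proportion times in-window patency among non-crossovers. Alternatively, set late non-crossover scans to missing and impute them with the method already named in SAP 6.4. Either route avoids over-weighting crossovers.
2. **A device-by-timing interaction**, reported as the risk difference with 95% CI for in-window and for late scans, and not judged on its low-powered p-value.
3. **A table of scan day by arm.**

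Also state that adjudicated crossovers without a CCTA stay in as events, in line with SAP 4.2, and say how their delay value is set in the covariate model.

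The cost is SAP wording and one extra table, with no new data. The in-window estimate has a wider interval and selects on a post-randomisation variable, so it belongs beside the all-scan result and should not replace it.
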